8. TRIAL ASSESSMENTS

8.1. Administration of demographics questionnaire

All patients will be asked to complete a demographics booklet at baseline. This booklet is based on the DISTINCT project to monitor inclusivity of clinical research. This will be administered as a separate paper booklet and may become available as an electronic questionnaire at later stage of the study.

8.2. Administration of (e)PRO booklets

All patients who have consented to complete PRO questionnaires will be asked to complete questionnaires at pre-treatment, then from the start of radiotherapy at weeks 1, 2, 3 and 5, 3 months and annually from 1-5 years.

Patients in the early side-effects sub-study will additionally be asked to complete questionnaires at weeks 4, 6 and 7.

It is anticipated that the option of electronic completion (ePRO) will become available whilst the trial is recruiting. Patients will be asked at randomisation whether they prefer electronic or paper questionnaire completion. The FAST-Forward Boost trials office will inform the sites and recruited patients who prefer electronic PRO completion when it is available.

Paper PRO completion

Pre-treatment (baseline) questionnaires will be in a booklet and handed out in the clinical centre by a member of staff. Patients will be asked to complete the questionnaires after a full explanation of the study and after giving informed consent. They should be completed before first radiotherapy treatment and, ideally, before patient is informed of treatment allocation, to avoid the possibility of bias. It is the responsibility of the clinical centre to ensure the completed pre-treatment booklet is sent to the trials office.

Patients will be asked to complete subsequent questionnaires at the timepoints described above. The booklet containing questionnaires for weeks 1, 2, 3 and 5 will be given to the patient at the start of radiotherapy. Sites should remind patients to complete their trial questionnaires on a regular basis. For UK patients all other booklets will be posted to the patient's home from the trials office. Patients will be sent a pre-paid envelope to return each completed booklet to the FAST-Forward Boost trials office (UK only). For international sites all booklets will be administered by the site or national coordinating group.

Early side-effects sub-study

Patients taking part in the early side-effects sub-study will be given a booklet containing questionnaires for weeks 1-7 from the start of radiotherapy and be asked to return the completed booklet to the trials office in

the pre-paid envelope. Sites should regularly remind patients to complete their trial questionnaires on a weekly basis.

Questionnaires for later timepoints will be posted directly to the patient from the trials office.

Electronic PRO completion (ePRO)

When ePRO is available, patients who have indicated a preference for electronic completion will be provided with login details and will receive email notifications and reminders when a questionnaire needs completing following the schedule outlined above.

8.3. PRO responses

The hospital team will not be informed of individual patient responses except where a patient participating in the early side-effects sub-study has a clinically significant score on the HADS, as these patients should be further assessed clinically. The early side-effects sub-study Patient Information Sheet explains that high HADS anxiety/depression scores will be passed on to their doctor. The FAST-Forward Boost trial team will contact the patient's hospital team in these cases.

8.4. Pre-treatment Assessments

The following baseline pre-treatment assessments should be conducted after consent to participate in FAST-Forward Boost, unless they are part of standard of care, and before first treatment of radiotherapy:

- Medical history (including specific risk factors for cardiovascular disease and radiotherapy toxicity).
- Weight and height measurement.
- Breast assessment (trial-specific as used in previous trials and Harvard-Harris scale).
- Lung toxicity assessment (RTOG).
- UK only: Demographic questionnaire completed by patient (including ethnic group, sex and gender, sexual orientation and caring responsibilities)
- Pre-treatment patient-reported outcomes (e)(PRO) health-related quality of life questionnaire booklet*(not mandatory), including:
 - EORTC QLQ-C30 and QLQ-BR23
 - Body Image Scale (BIS)
 - Fatigue (EORTC QLQ FA12)
 - EQ-5D-5L
 - Radiotherapy symptoms (breast & arm/shoulder trial specific, used in previous trials)
 - *For patients receiving treatment to IMC: oesophageal toxicity (PRO-CTCAE V5.0).*
- One blood sample (not mandatory) for those patients providing consent, ideally before radiotherapy starts but can be at any timepoint. If the patient is participating in the early-side effects substudy, see box below.

Additional pre-treatment assessments for EARLY SIDE-EFFECTS SUB-STUDY ONLY

- Health care professional (HCP) assessed skin, breast and oesophageal toxicity assessment (CTCAE V5.0)
- Patients should be given the substudy specific pre-treatment (e)PRO booklet*, containing the following additional questionnaires:

- Patient assessed skin, breast, and oesophageal toxicity assessment (PRO-CTCAE V5.0 and trial specific questions as used in previous trials).
- Patient reported outcome Hospital and Anxiety Depression Scale (HADS)
- For patients who have consented to the translational substudy and early side effects translational substudy, the 1st blood sample **must** be taken **prior to** and as close as possible to the start of radiotherapy treatment.

*NB: Ideally, pre-treatment PRO questionnaires should be completed prior to the patient being aware of treatment allocation. If using ePRO, all questionnaires will be provided electronically by the ICR-CTSU office.

8.5. Timing of on-treatment assessments

Participants in the Control Group will receive radiotherapy over three weeks. Participants in Test Groups 1 and 2 will receive radiotherapy over one week. Assessments should be completed by all participants at the end of each week from the start of radiotherapy:

- Participants in the Control Group will complete these assessments whilst receiving treatment at the end of weeks 1, 2 and 3 (i.e. at fraction 5, at fraction 10 and at final treatment).
- For participants in the Test Groups, the week 1 assessment will be completed at the end of their treatment week (i.e. at fraction 5), and then week 2 and week 3 assessments will take place 7 days and 14 days after their final treatment, respectively.

In the unlikely event of treatment interruptions, the timing of these weekly assessments should remain scheduled in accordance with the originally planned start and end dates.

8.6. On-treatment and end of treatment assessments

At the beginning of their radiotherapy treatment, all participants who have consented to complete PRO questionnaires should be given the **“On-Treatment and End of Treatment Assessments” (e)PRO questionnaire booklet**, containing the following:

At the end of weeks 1, 2 and 3:

- Patient-reported outcome of fatigue (EORTC QLQ FA12).
- Patient-reported outcome of health-related quality of life (EQ-5D-5L).
- Patient-reported out of pocket expenditure questionnaire (UK only).

At the end of week 5:

- Patient-reported health-related quality of life (EORTC QLQ-C30 and QLQ-BR23)
- Patient-reported Body Image Scale (BIS)
- Patient-reported outcome of fatigue (EORTC QLQ FA12)
- *For participants receiving IMC radiotherapy:* Patient reported oesophageal toxicity (PRO-CTCAE V5.0).

Sites should remind patients to complete their trial questionnaires within the booklet at the end of every applicable week.

Additional assessments Week 1 to 7, for EARLY SIDE-EFFECTS SUB-STUDY ONLY

At the beginning of their radiotherapy treatment, patients taking part in the Early Side Effects Sub study should be given the sub study specific **“On-Treatment and End of Treatment Assessments” (e)PRO booklet**, containing the following additional questionnaires:

- **At the end of weeks 1 to 7:** Patient assessed skin, breast, and oesophageal toxicity assessment (PRO-CTCAE V5.0 and trial specific questions as used in previous trials)

- **At the end of week 7 only:** Patient reported outcome of fatigue (EORTC QLQ FA12).

Additionally, the following assessments should be performed **in person**:

At the end of week 1

- HCP assessed skin, breast and oesophageal toxicity assessment (CTCAE V5.0)
- Blood samples (for patients who have given consent):
 - **Test group patients:** 2nd blood sample, taken ideally just after fraction 5.

At the end of week 3

- HCP assessed skin, breast and oesophageal toxicity assessment (CTCAE V5.0)
- Blood samples (for patients who have given consent):
 - **Control group patients:** 2nd blood sample, taken ideally just after fraction 15.
 - **Test group patients:** 3rd blood sample.

At the end of week 5

- HCP assessed skin, breast and oesophageal toxicity assessment (CTCAE V5.0)
- Blood samples (for patients who have given consent):
 - **Control group patients:** 3rd blood sample.

At the end of week 7

- HCP assessed skin, breast and oesophageal toxicity assessment (CTCAE V5.0).

Timing of assessments (assuming no treatment interruptions*):

	Control Group	Test Group
Week 1	At fraction 5	At fraction 5
Week 2	At fraction 10	7 days after final fraction
Week 3	At fraction 15	14 days after final fraction
Week 4	7 days after final fraction	21 days after final fraction
Week 5	14 days after final fraction	28 days after final fraction
Week 6	21 days after final fraction	35 days after final fraction
Week 7	28 days after final fraction	42 days after final fraction

*In the unlikely event of treatment interruptions, the timing of these weekly assessments should remain scheduled in accordance with the originally planned start and end dates.

Month 3

The following assessments should be conducted at 3 months after the start of radiotherapy for all participants:

- Lung toxicity assessment (RTOG) (*can be conducted by remote consultation*)
- Participants who have consented to complete PRO questionnaires will be sent/given a Follow-up (e)PRO booklet, including the following questionnaires (*for UK participants this will be coordinated by ICR-CTSU*):
 - EORTC QLQ-C30 and QLQ-BR23
 - Body Image Scale (BIS)
 - Fatigue (EORTC QLQ FA12)
 - EQ-5D-5L

- Radiotherapy symptoms (breast & arm/shoulder trial specific, used in previous trials).
- Patient reported health care resource use (UK only)

Additional assessments at month 3 for EARLY SIDE-EFFECTS SUB-STUDY ONLY

Patients will be sent the sub study specific “Follow Up Assessments – 3 months” (e)PRO booklet, containing the following additional questionnaires (*this will be coordinated by ICR-CTSU*):

- Patient assessed skin, breast, and oesophageal toxicity assessment (PRO-CTCAE V5.0 and trial specific questions as used in previous trials).

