10.3. Endpoint Definitions

Primary endpoint

The primary endpoint is ipsilateral breast tumour recurrence at 5 years, defined as either invasive or non-invasive ipsilateral tumour recurrence in the breast, including tumours considered to be new primaries by virtue of biology or location. Kaplan-Meier estimation will be used, with observations censored at death or most recent follow-up assessment for those patients without an event.

Secondary endpoints

- Patient-reported acute radiotherapy adverse effects (up to 3 months post-treatment*), with a focus on skin, breast, and oesophageal toxicity (PRO-CTCAE v5.0 and trial-specific assessments).
- Patient-reported late effects (between 1- and 5-years post-treatment*), with a focus on breast and arm/shoulder symptoms, using both standard instruments (EORTC QLQ BR-23) and trial-specific assessments.
- Patient-reported fatigue and quality of life (EORTC QLQ FA12, QLQ C30, QLQ BR-23, Body Image Scale (BIS), EQ5D-5L), measured throughout follow-up.
- Clinician-reported acute skin and oesophageal toxicity (CTCAE v5.0, up to 7 weeks post-treatment*) and breast oedema (trial specific, used in previous trials).
- Clinician-reported lung toxicity (RTOG, 3- and 12-months post-treatment*).
- Clinician-reported late normal tissue effects and cosmetic outcome (between 1- and 5-years post-treatment*), assessed with tools developed in previous breast radiotherapy trials and the Harvard Harris scale.

- Clinician-reported other late radiotherapy adverse events (between 1- and 5-years post-treatment*), including arm and breast lymphoedema, sensori-motor symptoms, symptomatic rib fracture, symptomatic lung fibrosis and ischaemic heart disease.
- Recurrence-free survival, defined as time to the first of: invasive ipsilateral breast tumour recurrence, invasive loco-regional recurrence, distant recurrence or death from any cause. Observations will be censored at most recent follow-up assessment for those patients without an event.
- Breast cancer-related survival, defined as time to breast cancer death. Observations will be censored at death due to other cause or most recent follow-up in those patients without an event.
- Overall survival, defined as time to death from any cause, with observations censored at most recent follow-up for surviving patients.
- Cost-effectiveness, based on health economic analysis which incorporates data on patient-reported health resource usage and health status (EQ-5D-5L).

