**Follow-up times are measured from treatment start date.*

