The primary endpoint will be presented by trial arm using Kaplan-Meier curves; estimated 5-year event rates will be given along with 95% confidence intervals. The treatment effect from each pairwise comparison will be presented as an absolute difference, by applying the hazard ratio (and corresponding 95% confidence interval) to the control group 5-year event-free estimate. This will be the primary assessment of non-inferiority (whether or not the upper limit of the confidence interval exceeds 2%). Additionally, the hazard ratio will be used to present treatment effect on a relative scale, presented with a 95% confidence interval. Hazard ratios will be derived from Cox proportional hazard regression models. The primary analysis will be unadjusted, but estimates will also be presented after adjustment for factors used in the randomisation algorithm and other important prognostic factors (which will be pre-specified in the analysis plan). As noted above, a sensitivity analysis based on a per protocol population will also be reported. The proportional hazards assumption will be checked and, if violated, appropriate alternative methods will be applied.

Analysis of secondary endpoints

PRO questionnaires will be scored using published manuals, including methods for handling missing data. Analyses of both patient-reported and clinician-reported toxicity data will follow methods established in previous breast radiotherapy trials(6, 10, 16, 39, 40) (11) and will account for multiple testing by adjustment of significance levels. Frequencies of early and late toxicities will be summarised at each time point/period and compared between treatment groups using chi-squared test or Fisher's exact test as appropriate. Where appropriate, longitudinal models (e.g. generalised estimating equations) including all assessments over follow-up, and survival analyses of time to first moderate/marked adverse effect will be carried out with comparisons between treatment groups, adjusting for balancing and other factors (for example, pre-treatment HADS score) where relevant. Event rates at key time points will be reported with 95% confidence intervals. For the analysis of late radiation effects on normal tissues the two test groups will be compared to estimate by interpolation the 5Fr schedule equivalent to control in terms of adverse effects.

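### Main-trial IMC patients have one post-baseline oesophageal self-report, at week 5, which falls 14 days after the last fraction in control but 28 days in the test groups, so the comparison mixes schedule effect with recovery time

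*Protocol*

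**What the plan says.** Section 8.4 gives a pre-treatment measurement in the main trial: "For patients receiving treatment to IMC: oesophageal toxicity (PRO-CTCAE V5.0". Section 8.6 then lists "Patient reported oesophageal toxicity (PRO-CTCAE V5.0" for IMC patients at the end of week 5. The main-trial questionnaires for weeks 1 to 3 and for month 3 do not include it. Clinician CTCAE grading of the oesophagus is listed for the sub-study only.

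Weeks are counted from the start of radiotherapy, which lasts three weeks in control and one week in the test groups (section 8.5). The timing table in section 8.6 gives the consequence for week 5: "14 days after final fraction" in control and "28 days after final fraction" in the test groups. Section 10.3 states the convention openly: "Follow-up times are measured from treatment start date".

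Section 10.3 defines the acute patient-reported endpoint "with a focus on skin, breast, and oesophageal toxicity". Section 10.4 says that toxicity frequencies will be "summarised at each time point/period and compared between treatment groups".

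**The concern.** With a single post-baseline measurement, a difference between arms at week 5 can come from the schedule, from the extra 14 days since the last fraction in the test groups, or from both. The data cannot separate these. A real excess with the 1-week schedules could be hidden, or a difference could appear where toxicity is the same.

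The analysis plan cannot repair this. A matched pair at 14 days needs test week 3 with control week 5. A matched pair at 28 days needs test week 5 with control week 7. In the main trial the item is given at neither week 3 nor week 7.

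The item matters because swallowing difficulty is an expected toxicity of nodal radiotherapy (section 9.4), and because section 1.1 says IMC patients were not in the earlier 1-week nodal sub-study.

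**Working it through.** **1. The protocol's own intervals.** Days since the final fraction = (assessment week − last treatment week) × 7.
- Control, week 5: (5 − 3) × 7 = 14.
- Test, week 5: (5 − 1) × 7 = 28.

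Both match the timing table. The gap is 14 days. In the schedule table (section 8.11) the extracted columns are visibly shifted, so it is not relied on here.

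**2. Direction.** Assume the same bell-shaped symptom profile in every arm, timed from the final fraction, with peak at day p and standard deviation s. The ratio of test (day 28) to control (day 14) is then exp[14(p − 21)/s²]. For s between 7 and 14 days:

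| Peak, days after final fraction | Test/control ratio at week 5 |
|---|---|
| 0 | 0.00 to 0.22 |
| 7 | 0.02 to 0.37 |
| 14 | 0.14 to 0.61 |
| 21 | 1.00 |
| 28 | 1.65 to 7.39 |

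The sign changes at day 21. The profile is an assumption. The only acute time course in the protocol is for skin and fatigue, with a peak 2 to 4 weeks after radiotherapy (section 1.1). That range contains both day 14 and day 28, and its midpoint is day 21.

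**3. Numbers of patients.** Section 10.1 expects 10–15% of 4830 to receive IMC radiotherapy. At 10% this is 483 patients, or 161 per arm. At 15% it is about 724, or 242 per arm.

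**4. How often timing alone would give a significant result.** Assume identical toxicity, full questionnaire response, one test group against control and an unadjusted two-sided 5% test. The probability is Φ[(|p1 − p2| − 1.96·SE0)/SE1], where SE0 uses the pooled proportion and SE1 the separate ones. For 20% against 10% with 161 per arm:
- SE0 = √(0.15 × 0.85 × 2/161) = 0.0398.
- SE1 = √((0.16 + 0.09)/161) = 0.0394.
- (0.10 − 1.96 × 0.0398)/0.0394 = 0.56, and Φ(0.56) = 0.71.

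The same formula gives:

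| Symptoms at day 14 → day 28 (assumed) | 161 per arm | 242 per arm |
|---|---|---|
| 20% → 10% | 71% | 87% |
| 20% → 14% | 30% | 42% |
| 10% → 5% | 40% | 55% |
| 10% → 7% | 16% | 22% |

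With 161 per arm and an illustrative 1% level, the first two rows fall to 47% and 13%. With an assumed 70% response (112 per arm, 5% level) they fall to 55% and 22%.

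**5. What the sub-study can supply.** It collects the item weekly in weeks 1 to 7, so both matched pairs exist there. If the 10–15% share applies, IMC patients number 0.10 × 345 ≈ 35 to 0.15 × 345 ≈ 52, or roughly 12 to 17 per arm.

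**The case against.** The strongest defence concerns the question being asked. Timing from the start of treatment is a declared convention, and the protocol prints the resulting intervals. Having fewer symptoms five weeks after starting is a real consequence of finishing sooner, and section 1.1 presents an earlier return to normal life as a benefit. This stands: the comparison by time from start is legitimate, the protocol does not contradict itself, and alignment on the end of treatment answers a different question. It does not remove the need for a second view, because with one time point the reader cannot tell recovery time from toxicity. The protocol already takes its second and third blood samples relative to the end of radiotherapy (sections 8.6 and 18.1), with the third at test week 3 and control week 5.

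Second, the sub-study has well-timed data and section 10.4 allows longitudinal models. This also stands, but for few IMC patients, and a model cannot align main-trial observations that were never collected.

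Third, the protocol's main safety concern in IMC patients is pneumonitis, which has its own powered analysis. The oesophageal item is one part of a secondary endpoint, in a minority of patients, with optional questionnaires and no decision rule. This stands and limits the weight of the point.

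A reader might infer that the week 5 comparison favours the 1-week schedules. The documents do not support that, because they give no oesophageal time course and the sign depends on when symptoms peak. A reader might also pool the two test groups. With 20% falling to 10%, that gives 84% (161 v 322) or 95% (242 v 483). Section 10.1 makes pairwise comparison the default, however, and pooling is not indicated for this item. Section 10.4 also adjusts significance levels for multiple testing.

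**Conclusion.** The point holds as a design weakness of modest weight. The 14-day difference in time since treatment is exact and comes from the protocol. After baseline, main-trial IMC patients have no other oesophageal self-report with which to correct for it. The direction is uncertain: the comparison may favour the 1-week groups if symptoms are resolving by day 14, and may go against them if the peak is later than about day 21.

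At the 10% IMC share, timing alone would give a significant pairwise difference in 16% to 71% of trials under the assumptions above. Symptom prevalence, its fall between day 14 and day 28, full response and the unadjusted 5% level are all assumed. Incomplete response or multiplicity adjustment lowers every figure. The primary endpoint and the pneumonitis analysis are unaffected.

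**What to change.** Add the oesophageal PRO-CTCAE item(s) to the week 3 questionnaire that IMC patients who consent to PROs already receive. Report the comparison at 14 days after the final fraction (test week 3 against control week 5) alongside the comparison by time from treatment start, and say which question each one answers. Neither needs to replace the other.

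Report fatigue (EORTC QLQ FA12) on the same alignment. It is already collected at weeks 3 and 5, so this needs no new data.

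The cost is a few extra items for 10–15% of patients, a revised booklet and one extra analysis. No new questionnaire date is needed. The change helps only patients who have not yet passed week 3, so it is worth more the sooner it is made.

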8.7. Post-treatment Follow-up

Year 1

The following post-treatment assessments should be conducted at 1 year after the start of radiotherapy and should be done in clinic:

- Breast assessment (trial-specific, as used in previous trials and Harvard-Harris scale).
- Lung toxicity assessment (RTOG).
- Late toxicity and adverse events (including lymphoedema).
- Assessment for recurrence and survival.
- Participants who have consented to complete PRO questionnaires will be sent/given a Follow-up (e)PRO booklet, including the following questionnaires (*for UK participants this will be coordinated by ICR-CTSU*):
 - EORTC QLQ-C30 and QLQ-BR23
 - Body Image Scale (BIS)
 - Fatigue (EORTC QLQ FA12)
 - EQ-5D-5L
 - Radiotherapy symptoms (breast & arm/shoulder trial specific, used in previous trials).
 - Patient reported health care resource use (UK only).

Year 2

Participants who have consented to complete PRO questionnaires will be sent/given a Follow-up (e)PRO booklet, including the following questionnaires (*for UK participants this will be coordinated by ICR-CTSU*):

- Patient-reported outcomes of health-related quality of life (QoL) including:
 - EORTC QLQ-C30 and QLQ-BR23
 - Body Image Scale (BIS)
 - Fatigue (EORTC QLQ FA12)
 - Radiotherapy symptoms (breast & arm/shoulder trial specific, used in previous trials).
- Patient reported disease status.

Year 3

The following post-treatment assessments should be conducted at 3 years after the start of radiotherapy and should be done in clinic:

- Breast assessment (trial-specific as used in previous trials and Harvard-Harris scale).
- Late toxicity and adverse events.
- Assessment for recurrence and survival.

- Participants who have consented to complete PRO questionnaires will be sent/given a Follow-up (e)(PRO) booklet, including the following questionnaires (*for UK participants this will be coordinated by ICR-CTSU*):
 - EORTC QLQ-C30 and QLQ-BR23
 - Body Image Scale (BIS)
 - Fatigue (EORTC QLQ FA12)
 - EQ-5D-5L
 - Radiotherapy symptoms (breast & arm/shoulder trial specific, used in previous trials).
 - Patient reported health care resource use (UK only).

Year 4

Participants who have consented to complete PRO questionnaires will be sent/given a Follow-up (e)(PRO) booklet, including the following questionnaires (*for UK participants this will be coordinated by ICR-CTSU*):

- Patient-reported outcomes of health-related quality of life (QoL) including:
 - EORTC QLQ-C30 and QLQ-BR23
 - Body Image Scale (BIS)
 - Fatigue (EORTC QLQ FA12)
 - Radiotherapy symptoms (breast & arm/shoulder trial specific, used in previous trials).
- Patient reported disease status.

Year 5

The following post-treatment assessments should be conducted at 5 years after the start of radiotherapy and should be done in clinic:

- Breast assessment (trial-specific as used in previous trials and Harvard-Harris scale)
- Late toxicity and adverse events
- Assessment for recurrence and survival
- Participants who have consented to complete PRO questionnaires will be sent/given a Follow-up (e)(PRO) booklet, including the following questionnaires (*for UK participants this will be coordinated by ICR-CTSU*):
 - EORTC QLQ-C30 and QLQ-BR23
 - Body Image Scale (BIS)
 - Fatigue (EORTC QLQ FA12)
 - EQ-5D-5L
 - Radiotherapy symptoms (breast & arm/shoulder trial specific, used in previous trials)
 - Patient reported health care resource use (UK only).

Mammograms should be performed post treatment as per standard of care.

Beyond Year 5

During the trial, the ICR-CTSU team aim to transfer the provision of longer-term follow-up data (including data to determine recurrence outcomes) from research sites to NHS routine data sources (and international equivalent where available), providing the patient has given consent to do so and the required information can be accessed from routine sources. This is intended to relieve the burden of longer-term follow-up on research sites, and as a move towards this, data collection in the eCRF is minimal for patients in whom no disease event has occurred. Where this data is not available from routine data sources, information will continue to be collected from research sites.

